4.3.2 Main analytical approach

Time to tolerization will be summarized using descriptive statistics of number of observations, mean, standard deviation, median, 25th and 75th quartiles, minimum, and maximum. Kaplan-Meier estimates for median, 25th and 75th quartiles will also be provided. A Kaplan-Meier plot showing percentage of patients who tolerized against time from the first ITI infusion will be generated. Patients not achieving ITI success during the ITI Period (48 weeks) will be censored at the latest time with positive inhibitor titer data for this analysis. The ITIFAS will be used.

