## 7.2.2. Immune Tolerance Induction Period

The first dose of rFVIIIFc ITI will be administered at the Baseline Visit, and treatment will continue until ITI success is declared or for a maximum of 48 weeks (12 months). The ITI regimen consists of rFVIIIFc 200 IU/kg/day ( $\pm$ 8 hours), which may be given as once-daily injections or divided into several injections per day at the discretion of the Investigator.

Subjects will visit the clinic 2 and 4 weeks after enrollment and then every fourth week until 48 weeks (12 months) or until a negative inhibitor ( $<0.6$  BU/mL) has been obtained. After the negative inhibitor results, visits will be scheduled every other week until ITI success or failure is declared.

The Investigator's assessment of ITI outcome will be based on results from the local laboratory. If the local laboratory results are inconclusive, the Investigator may use the central laboratory results to determine ITI outcome. During the ITI Period, subjects will undergo procedures and assessments at designated visits per [Table 1](#). Samples for inhibitor testing and assessment of FVIII activity levels will be analyzed at the local laboratory and at the central laboratory. Investigator treatment and assessment of inhibitor status will be based on results from the local laboratory. Negative inhibitor testing results must be confirmed (i.e., 2 consistent results at 2 consecutive assessments). See Section [7.2.2.2](#) for specific definitions of ITI outcomes.

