#### Treatment failure

Treatment failure is defined as fulfilling one of the following criteria:

- No downward trend of at least 20% in the inhibitor titer in a 6-month (24-week) period after the initial 3 months (12 weeks) during the ITI Period (assessed at the Week 36 [Month 9] Visit).
- Presence of a sustained positive inhibitor ( $\geq 0.6$  BU/mL) after 48 weeks (12 months) of ITI treatment.
- Negative inhibitor titer without achieving either of the 2 PK parameters of ITI success after 48 weeks (12 months) of ITI treatment:
  - $IR \geq 1.32$  IU/dL per IU/kg OR
  - $t_{1/2} \geq 7$  hours

Subjects who have been determined to have failed ITI will then proceed to the End of Treatment (EOT) Visit.

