#### Partial success

Partial success is defined as achieving negative inhibitor titer and one of the PK parameters of ITI success:  $IR \geq 1.32$  IU/dL per IU/kg OR  $t_{1/2} \geq 7$  hours.

The determination of partial success will be made only among subjects who have completed the maximum period of 48 weeks (12 months) of ITI treatment but do not fulfill the criteria for ITI success or treatment failure

Subjects who have been determined to have achieved only partial success will then proceed to EOT Visit.

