## 8. SELECTION OF SUBJECTS

### 8.1. Inclusion Criteria

To be eligible to participate in this study, candidates must meet the following eligibility criteria at the time of enrollment:

1. Ability of the subject or his legally authorized representative (e.g., parent or legal guardian) to understand the purpose and risks of the study and provide signed and dated informed consent and authorization to use protected health information in accordance with national and local subject privacy regulations
2. Male subjects of any age diagnosed with severe hemophilia A (as confirmed from the medical record)
3. Currently diagnosed with high-titer inhibitors (historical peak  $\geq 5$  BU/mL, according to medical records)
4. Previously treated with any pd-FVIII or recombinant conventional or Extended Half-Life FVIII
5. Canada specific requirements: See Appendix B.

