#### **16.2.2. Methods of Analysis**

##### **16.2.2.1. Primary Endpoint Analysis**

The primary endpoint of this study, time to tolerization with a maximum of 12 months (48 weeks) of ITI treatment, will be summarized descriptively using minimum, mean, standard deviation, median, 25th and 75th quartiles, and maximum. A Kaplan-Meier plot showing percentage of subjects who are tolerized against time from the first ITI infusion will also be generated. Subjects not achieving ITI success during the 12-month (48-week) ITI Period will be censored at the last observed time for this analysis. The ITIFAS will be used for this analysis.

CONFIDENTIAL

The information contained herein may not be used, disclosed, or published without the written consent of  
Bioverativ Therapeutics Inc.

Page 75

Descriptive statistics of the levels of rFVIIIFc inhibitors will be summarized longitudinally for all visits during the ITI Period.

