4.4.1.2 Main analytical approach

ITI success

The number and proportion of patients achieving complete ITI success, partial success, treatment failure, undetermined, or ongoing with ITI will be summarized.

The ITIFAS will be used for this analysis.

Occurrence of relapse after successful ITI

Occurrence of relapse will be summarized descriptively by calculating the proportions of patients who reach ITI success and later meet criteria of relapse during the Tapering Period, Follow-up Period, and the two Periods combined. The TPFAS will be used for this analysis.

Time to relapse will be defined as the duration between ITI success and time of relapse. Time to relapse from successful ITI will also be summarized descriptively for patients who relapsed during either the Tapering or Follow-Up Period.

Number of bleeding episodes during ITI, Tapering, and Follow-Up Periods

The number of bleeding episodes during ITI Period will be summarized by month using the ITIFAS. Descriptive statistics for annualized bleeding rate while the patients undergo ITI treatment will also be provided. The same analysis will be conducted by whether the bleeding episode is treated, and by type and location of bleeding episodes.

Patients will only be included in this analysis if they were observed for at least 90 days.

The annualized bleeding episodes will also be summarized for the Tapering and Follow-Up Periods using the TPFAS and by patient status of relapse. Detailed results based on whether a bleeding episode is treated, and type and location of bleeding episodes will also be provided.

Number of days away from work or school

If sample size permits ($n \geq 5$), number of days missed from school or work per month will be summarized descriptively for the ITI Period using the ITIFAS and for the combined Tapering and

Follow-Up Periods using the TPFAS. Otherwise, the data will be tabulated in individual patient listing only.

Number of hospitalization days

If sample size permits ($n \geq 5$), number of hospitalization days per year will be summarized descriptively for the ITI Period using the ITIFAS and for the combined Tapering and Follow-Up Periods using the TPFAS. Otherwise, the data will be tabulated in individual patient listing only.

Adherence

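### The SAP censors patients without ITI success at their last positive titer, not at the protocol's last observed time, which can only push the primary Kaplan-Meier curve up

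*SAP*

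**What the plan says.** Protocol 16.2.2.1 says that subjects who do not reach ITI success in the 48-week ITI Period "will be censored at the last observed time for this analysis". SAP 4.3.2 says that the same patients "will be censored at the latest time with positive inhibitor titer data for this analysis". SAP 4.1 has a general default for event times, the last on-study follow-up visit, but lets later sections override it, and 4.3.2 does. The SAP text supplied gives no reason for departing from the protocol. SAP 4.3.3 lists no sensitivity analysis.

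Tolerization needs all three of a negative titer, normal incremental recovery (IR) and a half-life of at least 7 hours, so a negative titer alone is not an event. Both documents foresee patients who turn negative without tolerizing:

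- **Partial success** (Protocol 7.2.2.2) is assigned "only among subjects who have completed the maximum period of 48 weeks (12 months) of ITI treatment".
- **Treatment failure** (Protocol 7.2.2.2) includes "Negative inhibitor titer without achieving either of the 2 PK parameters of ITI success after 48 weeks (12 months) of ITI treatment".
- **Early withdrawal** (SAP 4.4.1.1) has subcategories for a negative titer with and without normal IR.

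These patients remain under observation. Protocol 7.2.2 says: "After the negative inhibitor results, visits will be scheduled every other week until ITI success or failure is declared".

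**The concern.** A patient who is negative but short on IR or half-life is still at risk of the event and is being checked for it every two weeks. The SAP rule removes that patient from the risk set back to the last positive titer. A patient who later succeeds keeps the same negative-titer time in full. Whether the time counts therefore depends on the later outcome, which makes the censoring informative.

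At stake are the Kaplan-Meier median, quartiles and plot of the only primary endpoint. With about 17 patients, a few such cases can move them, always in the favourable direction.

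There is also a hypothetical edge case. The inclusion criterion reads "Currently diagnosed with high-titer inhibitors (historical peak" of at least 5 BU/mL, and no minimum titer is set at Screening or Baseline. A patient without success who had no positive on-study titer would have no usable post-baseline censoring date.

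**Working it through.** The documents give no expected Kaplan-Meier value, so there is no planned figure to reproduce. The check has two parts: direction, then size.

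**Direction.** The percentage tolerized is 1 − S(t), with S(t) = Π(1 − dᵢ/nᵢ). The events dᵢ are the same under both rules. The last positive titer is never later than the last observed time, so each nᵢ under the SAP rule is no larger than under the protocol rule. Each factor is then equal or smaller, and 1 − S(t) is equal or larger at every t. Simulation agrees: in 200,000 random data sets of 10, 17 or 30 patients, the SAP rule never gave a lower percentage or a later quartile.

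**Size.** From the documents: 17 patients (Protocol 16.1), a 48-week limit and the possibility of failure at Week 36. Event times, the number of negative-but-not-tolerized patients and their last positive weeks are assumed. Events precede censorings at ties. A quantile is the first time the curve reaches the stated percentage.

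*Example 1.* There are 8 successes, at weeks 12, 14, 16, 18, 22, 26, 32 and 44. Three patients fail at Week 36, one withdraws at week 10 and five are followed to week 48.

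- Protocol rule: 16 are at risk from week 12. Seven events by week 32 give S = 9/16. Three leave at Week 36, so 6 are at risk at week 44. S = 9/16 × 5/6 = 0.469, or 53.1% tolerized.
- SAP rule, with three of the five negative and last positive at weeks 12, 20 and 28: S = 15/16 × 11/14 × 8/10 × 6/7 × 2/3 = 0.337, or 66.3% tolerized.

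| Negative, not tolerized (last positive week) | SAP rule, Week 48 | Protocol rule, Week 48 |
|---|---|---|
| none | 53.1% | 53.1% |
| one (20) | 56.4% | 53.1% |
| two (12, 20) | 61.3% | 53.1% |
| three (12, 20, 28) | 66.3% | 53.1% |
| three, late (40, 44, 46) | 55.0% | 53.1% |
| three, on or after the last event (44, 46, 46) | 53.1% | 53.1% |

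In every row the first quartile stays at 18 weeks and the median at 44. With the last event at week 34 instead of 44, the three-patient case (12, 20, 28) gives 57.9% against 50.0%.

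Taking every combination of last positive weeks from 0, 2, 4, 8, …, 44 in Example 1:

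| Such patients | Combinations | Gap at Week 48, points (median) | Median moves from 44 to 32 weeks |
|---|---|---|---|
| 1 | 13 | 0 to 4.2 (3.2) | 0 |
| 2 | 91 | 0 to 9.4 (6.9) | 10 |
| 3 | 455 | 0 to 16.1 (12.6) | 173 |

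*Example 2, complete follow-up.* There are 10 successes, at weeks 12, 16, 20, 24, 28, 32, 34, 38, 40 and 44. Three patients are negative but not tolerized (last positive at 12, 16 and 20), and four are still positive at week 48.

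- Protocol rule: S = 7/17, so 58.8% tolerized, equal to the crude 10/17. First quartile 28 weeks, median 40.
- SAP rule: S = 16/17 × 14/15 × 12/13 × 4/11 = 0.295, so 70.5% tolerized. First quartile 24 weeks, median 38.

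With nobody lost to follow-up, the Kaplan-Meier percentage should equal the crude proportion. Under the SAP rule it does not.

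**The case against.** The strongest reply concerns size. The estimates SAP 4.3.2 lists are the median and quartiles; the Week 48 percentage can only be read off the plot. In the six Example 1 scenarios no listed estimate moves, and the first quartile never moves in the enumeration. The median shifts there need mostly early last positives: from week 12 onward they occur in 0 of 9, 0 of 45 and 15 of 165 combinations, and from week 24 onward in none. The combinations are weighted equally, so the median gaps are not expected biases. Protocol Table 1, footnote 1, also warns that titers fluctuate, and a later positive titer would narrow the gap. The study is descriptive, and SAP 4.3.4 plans a patient listing from which a careful reader could spot the problem.

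All of that is correct and limits the likely harm. It does not remove the contradiction or its one-sided direction, and Example 2 shows that listed estimates can move. A listing does not correct a published curve.

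A second reply is that the last positive titer is the last time a patient is known not to be tolerized. That holds only while the titer stays positive, when the two rules nearly coincide anyway. After that, the scheduled titer, IR and half-life assessments are what establish whether tolerization has occurred.

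The edge case of no on-study positive titer stays hypothetical: the criterion also requires a current diagnosis, and nothing suggests such a patient is likely.

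**Conclusion.** The concern holds. SAP 4.3.2 contradicts Protocol 16.2.2.1 on censoring for the primary endpoint and discards observed event-free time according to later outcome. The direction is a mathematical result: the curve can only rise or stay the same, and its quartiles can only shorten or stay the same.

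The size rests on assumed event times, on how many patients are negative but not tolerized, and on their last positive dates. In the 17-patient examples the Week 48 gap runs from nil to 16.1 points with up to three such patients, and the median shifts in some configurations only. Patients still positive at their last assessment are essentially unaffected.

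The effect is confined to the Kaplan-Meier output. The descriptive times among tolerized patients do not change. Nor does the outcome table of SAP 4.4.1.2, which reads: "The number and proportion of patients achieving complete ITI success, partial success, treatment failure, undetermined, or ongoing with ITI will be summarized".

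**What to change.** Replace the censoring sentence in SAP 4.3.2 with: *Patients not achieving ITI success during the ITI Period will be censored at their last ITI-Period assessment of tolerization status (inhibitor titer, IR or half-life), at most Week 48.*

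This makes the protocol's last observed time specific. The Week 48 cap fits Protocol Table 1, footnote 1, which dates a late-confirmed negative titer to the first value within the 48 weeks.

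The cost is one SAP sentence and minor reprogramming, with no new data. The curve may look less favourable.

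Optional, and separate from this error: a sensitivity analysis that keeps declared treatment failures, including those at Week 36, event-free in the risk set to Week 48.

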4.3.3 Sensitivity analysis

Not applicable.

4.3.4 Supplementary analyses

Additional analyses associated with primary endpoint

Time to negative titer, time to normal incremental recovery, and time to $t_{1/2} \geq 7$ hrs will be summarized using descriptive statistics for patients who meet the criteria for negative inhibitor, normal recovery, and $t_{1/2} \geq 7$ hrs, respectively. Individual patient listing tabulating outcome of ITI treatment, duration on ITI, times to negative inhibitor titer, normal recovery, and tolerization, duration in Tapering Period, duration in Follow-up Period, status of relapse, and duration from ITI success to relapse will be provided.

Factor activity levels from local and central laboratories will be tabulated in individual patient listing by study visit and time points of blood sample. The associated IR in IU/dL per IU/kg, $t_{1/2}$, and the investigator's assessment on whether a patient has met the criteria of IR and $t_{1/2}$ for ITI success will also be tabulated.

Exploratory analysis for the final data

Agreement between local and central laboratory results on the determination on negative titer, normal IR and $t_{1/2} \geq 7$ hrs for ITI success will be summarized. Scatter plots for inhibitor titer will be presented for the ITI period, showing the local laboratory results on the x-axis and the central laboratory results on the y-axis. A line crosses diagonal will be plotted to indicate perfect correlation. Scatter plots for IR in IU/dL per IU/kg and $t_{1/2}$ will be provided by study period.

Time to negative inhibitor

This is defined as the number of days from the first infusion of ITI with rFVIIIFc to the date of first negative titer with a subsequent confirmatory negative titer associated with ITI success.

Time to normal IR

This is defined as the number of days from the first infusion of ITI with rFVIIIFc to the date of first normal IR with a subsequent confirmatory normal IR associated with ITI success.

Time to half life ≥ 7 Hours

This is defined as the number of days from the first infusion of ITI with rFVIIIFc to the date of $t_{1/2} \geq 7$ hours.

Time from negative inhibitor titer to $t_{1/2} \geq 7$ hours

This is defined as the number of days from the date of confirmed negative inhibitor titer to the first date of $t_{1/2} \geq 7$ hours.

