4.3 PRIMARY ENDPOINT(S) ANALYSIS

4.3.1 Definition of endpoint(s)

The primary endpoint of this study is time to tolerization with a maximum of 48 weeks (12 months) of ITI treatment offered in the study (tolerization defined as inhibitor titer <0.6 BU/mL, rFVIIIFc incremental recovery [IR] $\geq 66\%$ of the expected IR, and $t_{1/2} \geq 7$ hours).

Negative inhibitor

Inhibitor titer value <0.6 BU are considered negative. To confirm that a patient's inhibitor titer has reached negativity, a consecutive second sample with a titer value <0.6 BU at the next visit is required.

Results from local lab will be used for this determination. If the local lab results are not available, the results from the central lab will be used. Occurrence and date of negative titer associated with ITI success will be recorded in the eCRFs by the investigator.

Normal incremental recovery (IR)

IR ≥ 1.32 IU/dL per IU/kg ($\geq 66\%$ of the expected IR 2 IU/dL per IU/kg) is considered normal IR. To confirm the occurrence of normal IR, a consecutive visit with a normal IR is required.

Results from local lab will be used for this determination. If the local lab results are not available, the results from the central lab will be used. Occurrence and date of normal IR will be recorded in the eCRFs by the investigator.

Half life ≥ 7 Hours

Achieving $t_{1/2} \geq 7$ hours is the final PK goal of the ITI treatment. Results from local lab will be used for this determination. If the local lab results are not available, the results from the central lab will be used.

Occurrence and date of $t_{1/2} \geq 7$ hours will be recorded in the eCRFs by the investigator.

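### SAP 4.3.4 ties time to negative titer and time to normal IR to later ITI success, in conflict with its own description of who is summarized, so patients who reach the milestone but never tolerize may get no milestone time

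*SAP*

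**What the plan says.** SAP 4.3.4 defines three milestone times, each counted from the first ITI infusion.

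- Time to negative inhibitor ends at the first negative titer "with a subsequent confirmatory negative titer associated with ITI success".
- Time to normal IR ends at the "date of first normal IR with a subsequent confirmatory normal IR associated with ITI success".
- Time to half-life carries no such clause: "This is defined as the number of days from the first infusion of ITI with rFVIIIFc to the date of $t_{1/2} \geq 7$ hours".

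The opening of the same section says who is summarized. The times "will be summarized using descriptive statistics for patients who meet the criteria for negative inhibitor, normal recovery" and half-life, each group taken by its own criterion. SAP 4.3.1 sets out the first two criteria as two consecutive qualifying results (titer below 0.6 BU; IR of at least 1.32 IU/dL per IU/kg). Neither requires later ITI success.

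On data capture, SAP 4.3.1 says "Occurrence and date of negative titer associated with ITI success will be recorded in the eCRFs by the investigator". The matching sentence for normal IR has no success condition.

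SAP 4.1 gives the general rule for event times: descriptive statistics among patients with the event, plus Kaplan-Meier estimates on the whole ITIFAS, with non-events censored at the last on-study follow-up visit. SAP 4.3.4 repeats only the descriptive part.

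**The concern.** A time to negative titer should end when the titer turns negative. Here the definition also looks ahead to whether the patient later meets the IR and half-life criteria.

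The documents expect patients who reach the milestone without tolerizing. Partial success (SAP 4.4.1.1) is a negative titer plus one PK criterion. The early-withdrawal category in the same section has subgroups for negative titer, and for negative titer with normal IR. Protocol 7.2.2.2 counts a negative titer with neither PK criterion at 48 weeks as treatment failure. By the opening of 4.3.4 these patients belong in the summary if their result was confirmed; by the definition they have no value to contribute. A programmer has to choose, and with up to 17 subjects (Protocol 16.1) or up to 30 (SAP 2) the choice can move a median.

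**Working it through.** The plan states no figure to reproduce: the study is descriptive, and no milestone time is a design input. The check has three parts.

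**1. Latest milestone that can still become success.** Inputs: the first IR sample is drawn at the confirmatory-titer visit and half-life is tested only after two normal IRs (Protocol Table 1, footnotes 13 and 14). Visits after the first negative are 2 weeks (±3 days) apart (Table 1), and the ITI Period is capped at 48 weeks (Protocol 7.2.2). With the first negative at week T:

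- confirmation and first IR at T + 2, second IR at T + 4, half-life at T + 6
- latest first negative: 48 − 6 = Week 42
- latest first normal IR, with two more visits to go: 48 − 4 = Week 44
- every −3-day window used: 336 − 3 × 11 = 303 days = Week 43.3 for titer; 336 − 2 × 11 = 314 days = Week 44.9 for IR

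Two provisions soften these limits: the confirmatory titer may fall after Week 48 (Table 1, footnote 1), and half-life may be tested at the EOT Visit (footnote 14). Under the literal definition, late milestones mostly cannot count, which pulls achievers-only times earlier.

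**2. Size under assumed distributions.** None of these inputs comes from the documents.

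*Model A.* Exponential time to negativity with 70% negative by Week 48, detected at Weeks 2, 4, 8, …, 48; lag to tolerization of 6 weeks plus an exponential; no reversion.

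| Mean extra lag (weeks) | True negatives without success | Achievers' median, success-linked | Achievers' median, any negative | All-patient median, success-linked | All-patient median, any negative |
|---|---|---|---|---|---|
| 6 | 19% | 16 | 20 | 32 | 28 |
| 12 | 30% | 16 | 20 | not reached | 28 |
| 20 | 43% | 12 | 20 | not reached | 28 |

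The success-linked curve fails to reach 50% because too few patients have the event: 0.70 × (1 − 0.30) = 0.49 and 0.70 × (1 − 0.43) = 0.40.

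*Model B.* Log-normal time to first confirmed negative; lag of 6 weeks plus a log-normal with median 6 weeks and log-SD 0.8; 48-week cap. In reversion rows, 30% of successes revert and turn negative again about 12 weeks later. All patients can tolerize in this table.

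| Median, log-SD | Reversion | Achievers' median: success-linked vs any | All-patient median: success-linked vs any |
|---|---|---|---|
| 8, 0.8 | none | 7.6 vs 7.9 | 8.0 vs 8.0 |
| 12, 1.2 | none | 9.0 vs 9.9 | 12.2 vs 11.9 |
| 20, 1.2 | none | 12.1 vs 14.1 | 20.7 vs 20.1 |
| 8, 0.8 | 30% | 9.6 vs 7.9 | 10.2 vs 8.0 |
| 12, 1.2 | 30% | 11.3 vs 9.9 | 14.7 vs 11.9 |
| 20, 1.2 | 30% | 14.2 vs 14.0 | 23.3 vs 20.1 |

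Without reversion the achievers' gap across Model B is about 0.2 to 2.2 weeks. If only 60% can tolerize, the all-patient success-linked medians without reversion become 18.1 weeks, not reached and not reached, against 8.0, 11.9 and 19.9 for any confirmed negative.

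In samples of 17 without reversion, the success-linked achievers' median was lower in 66% to 73% of replicates and higher in 15% to 22%. With 30% reversion it was higher in 66% to 70%.

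**3. A worked case of 17.** Suppose 14 turn negative at Weeks 2, 4, 4, 6, 8, 8, 12, 16, 20, 24, 28, 32, 36 and 40, three never do, and 10 of the 14 succeed. The median over all 14 is (12 + 16)/2 = 14.

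- The four non-tolerizers are the latest (28, 32, 36, 40): the success-linked median is (8 + 8)/2 = 8. The Kaplan-Meier median, the 9th event of 17, is 20 either way.
- They are mostly early (2, 4, 8, 36): the success-linked median is (16 + 20)/2 = 18. The Kaplan-Meier median moves from 20 to 32.

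**The case against.** The best defence is that the SAP does not clearly drop anyone. The group is described by the individual criterion, the normal-IR date is recorded without a success condition, and the contested phrase could be loose wording for the criteria that make up success. That stands in part: this is an internal contradiction, not a settled exclusion. It does not clear the SAP, because the definition of the variable still carries the clause, and for titer so does the eCRF sentence.

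A reader might infer that the milestones will simply look faster than they are. The documents do not support that as a general statement. SAP 4.1 already calls for Kaplan-Meier on the full ITIFAS, and there the clause makes milestones look slower. Footnote 1 of Protocol Table 1 calls fluctuating inhibitor levels common, so the clause may also pick out a later negative run.

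A reader might also infer that the results could not be set beside the 4.6 and 6.9 month medians that the protocol quotes for the high-dose arm of the randomized ITI study. The documents do not say which patients those medians cover, and they plan no formal comparison.

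The stakes are limited. These are supplementary descriptive summaries. Negative patients who do not tolerize still appear in the outcome categories and in the individual listing promised in SAP 4.3.4, and Protocol 16.2.2.1 summarizes inhibitor levels at every ITI visit. The 8-week gap needs a mean extra lag of 20 weeks; shorter lags in Model A give 4 weeks, one step on a 4-week visit grid. No simulated figure was produced for normal IR.

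**Conclusion.** The concern holds as a contradiction within the SAP that should be resolved. Read literally, the definitions of time to negative inhibitor and time to normal IR leave patients who reached the milestone without tolerizing with no value.

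The distortion runs both ways. It is most likely toward earlier times in the achievers-only statistics, the one summary that SAP 4.3.4 spells out. It is toward later times in any Kaplan-Meier estimate made under SAP 4.1. Reversion, or non-tolerizers who turn negative early, can also push the achievers' median later.

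Across the models without reversion, the achievers' median moves earlier by about 0 to 8 weeks. That range rests on assumed distributions for time to negativity and for the lag to tolerization. The low achievers-only medians relative to all patients (20 against 28 weeks in Model A for any negative) come from leaving out patients who never turn negative and would exist without the clause. The primary endpoint is unaffected.

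**What to change.** - In SAP 4.3.4, define time to negative titer and time to normal IR as first infusion to the first of two consecutive qualifying results, regardless of ITI outcome.
- Derive or record that date for every ITIFAS patient, and bring the eCRF sentence for negative titer in SAP 4.3.1 into line with the one for normal IR.
- Confirm in 4.3.4 that the Kaplan-Meier rule of SAP 4.1 applies to these milestones, and state the censoring date.
- Keep the success-linked times, if wanted, as a labelled subset.

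The cost is SAP wording and a few extra outputs. Titer and IR results are collected under the protocol in any case.
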